#### 9.1.2 Serious Adverse Events (SAE)

An SAE is any untoward medical occurrence that fulfils one or more of the following criteria:

- Results in death
- Is immediately life-threatening
- Requires hospitalisation or prolongation of existing hospitalisation
- Results in persistent or significant disability or incapacity
- Is a congenital abnormality or birth defect
- Intervention is required to prevent one of the above or is an important medical condition

##### SAEs exempt from reporting:

Any treatment which was elective or pre-planned for a pre-existing condition will not be considered to fulfil the criteria for 'serious' and will not be reported as a SAE for this trial. However, these data will be recorded as part of follow-up data collection in the participant questionnaires.

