## 6 TRIAL TREATMENTS

### 6.1 Details of the control intervention

For patients who have not benefited from NICE-recommended therapeutic exercise, usual care includes treatments such as pharmacological management, intra-articular steroid, and surgery [4]. Participants in the control arm will be instructed to access this care as they would if they were not involved in the trial.

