# 7 PARTICIPANT ELIGIBILITY CRITERIA

The CMT intervention has been positioned as a second-line intervention for people with knee OA which would be offered to NHS patients if they have tried therapeutic exercise and are dissatisfied with the outcome. We will therefore recruit patients with a clinical diagnosis (according to NICE) of knee OA [4] and who have

received NICE-recommended therapeutic exercise but who are dissatisfied with the outcome. The following inclusion/exclusion criteria will be used:

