### 9.2.4 Reporting SAEs

The trial team will liaise with the treating physiotherapist/participant to compile all the necessary information. Once the SAE form has been completed, causality assessments will take place as per section 9.2.2 above. SAEs that are deemed possibly, probably or definitely related to the trial intervention by causality assessor will be notified to the REC within 15 days.

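### The SAE exemption for elective treatment makes no exception for a condition that worsened after consent, so an elective admission for a knee that deteriorated during CMT gets no causality grading

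*Protocol*

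**What the plan says.** Section 9.1.2 of the protocol lists the seriousness criteria, among them "Requires hospitalisation or prolongation of existing hospitalisation". Under its sub-heading on exempt SAEs it then removes a class of events: "Any treatment which was elective or pre-planned for a pre-existing condition will not be considered to fulfil the criteria for" serious, and such treatment "will not be reported as a SAE for this trial". What is kept instead follows directly: "However, these data will be recorded as part of follow-up data collection in the participant questionnaires".

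Three other places determine what this means in practice.

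- Section 7 fixes the population: "We will therefore recruit patients with a clinical diagnosis (according to NICE) of knee OA". Knee OA is thus a pre-existing condition for all 252 planned participants.
- Section 9.2.2 asks for SAEs to be reported whatever their relationship to the intervention, but excludes those exempted in 9.1.2. It sets out the causality grading for SAEs.
- Section 9.2.4 makes the external notice depend on that grading: "SAEs that are deemed possibly, probably or definitely related to the trial intervention by causality assessor will be notified to the REC within 15 days".

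Section 6.1 shows that elective knee treatment is foreseeable in this population: "usual care includes treatments such as pharmacological management, intra-articular steroid, and surgery".

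**The concern.** An exemption for elective care of a pre-existing condition is ordinary and not wrong in itself. Its usual purpose is to keep out of the SAE listing procedures that say nothing about the trial treatment. This one lacks the limit that serves that purpose. It does not distinguish treatment of a condition following its expected course from treatment of a condition that got worse on study. That gap matters more here than in most trials, because the pre-existing condition is the one the intervention acts on.

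If CMT aggravated a knee and the patient was then admitted electively for it, that admission would be among the more relevant safety observations the trial could make. Under the wording it would not be an SAE by virtue of the hospitalisation, and nobody would be asked to judge whether CMT contributed. Section 9.2.3 intends any SAE with a causal relationship to the intervention to go to the REC. The exemption blocks that intention for this type of admission before the question of cause is asked. Serious adverse events and adverse events attributable to the trial are both listed secondary outcomes in section 3.3.

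**Working it through.** No published figure is in dispute, so the check traces one hypothetical event through the text: a CMT participant's knee deteriorates after consent and leads to an elective admission before six months.

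1. **Is it within the collection period?** Yes. Section 9.2.1 collects SAEs from consent to the six-month follow-up.
2. **Would the admission otherwise be serious?** Yes, through "Requires hospitalisation or prolongation of existing hospitalisation".
3. **Does the exemption apply?** Yes. Elective and pre-planned are joined by *or*, so an elective admission need not have been arranged before consent. Knee OA is pre-existing by eligibility. No other section narrows the rule.
4. **Does possible relatedness bring it back?** No. Section 9.2.2 applies the exemption regardless of relationship to the intervention.
5. **Is cause graded?** No. The grading in section 9.2.2 (Table 3) is defined for SAEs.
6. **Can the REC be notified under 9.2.4?** No. The notice needs an SAE graded possibly, probably or definitely related.
7. **Does the questionnaire reopen it?** Not by rule. Section 9.2.2 prompts follow-up when a questionnaire suggests an event that may be an SAE, and the exemption says this is not one.

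The same trace holds for another pre-existing musculoskeletal problem aggravated by CMT.

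**What still captures the deterioration:**

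- AE form, CMT arm (section 9.1.1). Only exacerbations of five days or less are exempt, so a longer worsening is recorded and checked for seriousness.
- Other seriousness criteria (section 9.1.2). Persistent or significant disability, or an important medical condition, could still make the worsening itself an SAE.
- Questionnaires, both arms (section 3.3). Surgery and hospital stays are recorded at 6 and 12 months.

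**What none of these routes supplies for the admission:** SAE status through hospitalisation, a stated causality procedure, and a reporting clock. The TSC, which also acts as the DMC, is shown an adverse-event summary but no unblinded outcome data. Surgery by arm recorded only in questionnaires would therefore not be expected to reach it as a safety signal during the trial.

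**Size.** The protocol gives no rate of elective admission. As a purely illustrative assumption, 2% to 10% of 126 per arm is 126 × 0.02 = 2.5 to 126 × 0.10 = 12.6. That range counts all elective admissions for any pre-existing condition. The relevant events are only those in the CMT arm that followed worsening during CMT and occurred within six months. Section 8.7 aims to start treatment within 7 weeks and deliver it over 7 to 9 weeks, so the target finish is no later than 7 + 9 = 16 weeks. Taking six months as about 26 weeks, roughly 26 − 16 = 10 weeks of SAE collection then remain. The relevant number is much smaller than the range and cannot be derived from the document.

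**The case against.** The strongest reply is that the protocol exempts a treatment and not a harm. A reader might infer that serious worsening of the knee under CMT vanishes from the safety record, so that the trial could report no related SAEs whatever happened. The documents do not support that. Worsening severe enough to lead to an elective admission would very likely last more than five days and so reach the AE form. CMT participants are asked about adverse events at each session, and AE summaries go to the TSC. The other seriousness criteria remain in force, as do emergency admissions.

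Second, the randomised comparison offers its own protection. Surgery and hospital stays are collected in both arms to 12 months, beyond the SAE window, and the protocol intends to look at knee replacement by arm. An excess after CMT could show there, perhaps more reliably than through case-by-case judgement.

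Third, surgery is part of the comparator. A reader might conclude that every elective admission arranged after consent should become an SAE. That would sweep in routine usual care and add noise to both arms.

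Fourth, the protocol reports over 200 people treated with versions of CMT and no adverse events, so the event in question may be rare.

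All four points stand, and they limit the finding. They do not remove it. None of these routes grades the cause of the admission or puts a clock on it, and the comparison by arm becomes available only at the end.

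**Conclusion.** The gap is real but narrow. Followed as written, section 9.1.2 prevents an elective admission between consent and six months, for a knee or other pre-existing musculoskeletal problem that deteriorated during CMT, from being an SAE through hospitalisation. It therefore also keeps the admission from causality grading and from REC notification. The loss is one of status, attribution and timeliness for the admission; the deterioration may still be recorded elsewhere.

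The number affected is probably small and cannot be estimated from the protocol. The conclusion does not depend on it, since one admission graded at least possibly related would call for the 15-day notice. It rests on two readings: that *elective* alone satisfies the exemption, and that no part of the protocol narrows it. This is a cheap improvement to a safety definition.

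**What to change.** Amend the exemption in section 9.1.2 so that it covers elective or pre-planned treatment only where the pre-existing condition has not worsened since consent beyond its expected course. Elective admissions that follow such worsening should go on the SAE form and through the causality assessment in section 9.2.2. Identify them in both arms from the six-month questionnaire, and in the CMT arm also from the AE forms. Align the wording of 9.2.2 and the SAE form guidance.

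The test should turn on worsening and not on the date the treatment was arranged, so that routine elective care belonging to the comparator stays out.

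The cost is one sentence in the protocol, a line of form guidance and probably a few extra SAE forms. Some will concern natural progression of OA and be graded unrelated, in which case no REC notice follows. Worsening will be ascertained less completely in the control arm, which is asked only once, at six months. Counts by arm should be read with that in mind.

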## 9.2 Recording Adverse Events and Reporting Serious Adverse Events

### 9.2.1 Recording and reporting period

Intervention (CMT) group: All AEs and SAEs (unless otherwise specified) occurring from the time of informed consent until the six-month follow-up time-point must be recorded and reported as appropriate. Participants will be asked about anything that might constitute a SAE at the six-month follow-up questionnaire (see 'Adverse event question') and will also be given the opportunity to identify any events at every face-to-face physiotherapy session or via email/letter (sent to the trial team) during the intervention period.

Usual care group: The usual care group will be asked about anything that might constitute a SAE during the six-month follow-up questionnaire only questionnaire (see 'Adverse event question'). It will not be possible to collect a comparison dataset for the usual care group within this period without contaminating usual care. This is a pragmatic study, and the participants will not be contacted during the intervention period, unlike the intervention group. It is important not to contact the usual care group more than is necessary so as not to introduce bias. We anticipate a low risk of adverse events arising from usual NHS care.

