## 8.7 Trial assessments and follow-up

The schedule of assessment is summarised in the table below. Following screening, eligible participants will return the consent form with the data access form (which provides permission to access x-ray data). Once received, the participant will then be asked to complete the Baseline data and diversity inclusivity survey, WOMAC [19], Pain catastrophizing scale (PCS) [25], Pain self-efficacy questionnaire (PSEQ) [26], Work Productivity and Activity Impairment Questionnaire (WPAI-OA) [27], EQ-5D-5L [28], healthcare resource utilisation along with the baseline qualitative survey (see 'Baseline qualitative survey'). As explained above, these data will be collected using the secure trial database. If participants prefer to provide data via a written document, they will be sent paper copies of every questionnaire in the post and provided with a stamped addressed envelope to return completed questionnaires.

Once baseline questionnaire data have been received, participants will be randomised. The timing of the two subsequent outcome data collection points will then be set based on the date of randomisation. We will aim for participants allocated to the CMT arm to begin treatment within 7 weeks of randomisation and for the intervention to be delivered over a 7-9 week timeframe. With this timeframe, all intervention sessions would be completed by four months (from the date of randomisation). However, we will allow some flexibility ensuring an upper limit of six months (from the date of randomisation) for completion of all intervention sessions. This will ensure that intervention is complete by the first follow-up outcome point. Follow-up data will be collected at 6 months and 12 months (from the date of randomisation), using the trial database or postal questionnaires (depending on participant preference). At 6 months and 12 months we will collect data using the same outcomes as baseline with the addition of the Global assessment of knee symptoms (GAKS) [24], which asks patients to recall change from

baseline (see Table 2 below). All data collected via postal questionnaire or minimum dataset will be entered into the trial database by a member of the research team who is blinded to group allocation.

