Following randomisation, the intervention coordinator (member of the research team) will liaise with participants in the intervention arm to schedule the intervention sessions. Once scheduled, participants will be sent a participant appointment information letter and schedule (see 'Group 1 Participant appointment letter'). Participants in the control arm will be sent the group 2 allocation letter (see 'Group 2 Allocation letter'). In some cases, research sites may use their own processes for booking and scheduling appointment. In this scenario, participants in the control arm will still be sent the same letter, however, participants in the CMT arm may receive the same information from their trust in a different format.

During the CMT treatment, the treating physiotherapists will keep a log of the number and length of appointments attended and will also record a weekly engagement score, as described in Section 6.5. Only attendance data will be used in the final analysis, with attendance of 6 (out of 7) sessions defined as achieving minimum adherence.

In some cases, it may be necessary to delay the collection of baseline data for up to 2 months from the point of consent. This may be necessary to facilitate scheduling of physiotherapy appointments for participants allocated to the CMT arm at research sites where there is limited capacity (due to physiotherapist availability) to deliver the intervention.

Table 2: Schedule of assessments

Assessment	Timepoint						
	Screening	Consent	Baseline	Intervention delivery (0-6 months)	6 months	12 months	13-14 months
Eligibility assessment	x						
Participant invitation	x						
Screening data	x						
Informed consent		x					
Data access form		x					
Baseline data and diversity and inclusion survey			x				
WOMAC			x		x	x	
GAKS					x	x	
PCS			x		x	x	
PSEQ			x		x	x	
WPAI-OA			x		x	x	
EQ-5D-5L			x		x	x	
Healthcare resource utilization			x		x	x	
Baseline qualitative survey			x				
Randomisation				x			
Physiotherapy sessions (CMT arm)				x			
Treatment log				x			
Adverse events				x	x		
Death				x	x	x	
Semi-structured interviews							x

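### Section 9.2.1 opens the CMT arm's AE/SAE window at consent, before randomisation, and gives no start for usual care, so SAEs from before randomisation can enter the CMT count

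*Protocol*

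**What the plan says.** All references are to the protocol.

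- **CMT window (section 9.2.1).** "Intervention (CMT) group: All AEs and SAEs (unless otherwise specified) occurring from the time of informed consent until the six-month follow-up time-point" are to be recorded and reported. CMT participants can raise events at every physiotherapy session and by email or letter. They also answer an SAE question at six months: "Participants will be asked about anything that might constitute a SAE at the six-month follow-up questionnaire".
- **Usual-care window (section 9.2.1).** "The usual care group will be asked about anything that might constitute a SAE during the six-month follow-up questionnaire only". No start date is given and non-serious AEs are not sought. The section explains the difference: "It will not be possible to collect a comparison dataset for the usual care group within this period without contaminating usual care".
- **Order of events (sections 8.4 and 8.7).** Consent comes first, then baseline data, then allocation: "Once baseline questionnaire data have been received, participants will be randomised". Section 8.7 adds that in some cases "it may be necessary to delay the collection of baseline data for up to 2 months from the point of consent". Section 8.8 allows two weeks of baseline reminders.
- **Follow-up clock (section 8.7).** "Follow-up data will be collected at 6 months and 12 months (from the date of randomisation").
- **Schedule (Table 2, section 8.7).** The adverse-event row is marked under intervention delivery (0-6 months) and at 6 months, and not at consent or baseline. Randomisation is marked in the intervention-delivery column.
- **Use of the data.** Section 3.3 lists two separate safety outcomes: AEs attributed to the trial, and SAEs with no attribution limit. Section 3.1 includes adverse events among the outcomes for which treatment effects are to be estimated. Section 9.2.2 requires SAEs to be reported whatever their cause, apart from the exempt categories.

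**The concern.** At consent nobody belongs to a CMT group. A window that opens at consent for that group alone can only be applied backwards, once allocation is known. The six-month end point, by contrast, runs from randomisation. The CMT window is therefore longer than six months by the consent-to-randomisation lag, and the extra time lies wholly before treatment assignment.

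An event in that interval cannot be an effect of allocation. If it is tabulated in one arm under a rule the other arm lacks, the SAE comparison is no longer purely between randomised groups over the same period, and the direction is against CMT. The SAE outcome is where this matters, because it has no attribution limit: an SAE judged unrelated still counts.

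The point concerns only where the window starts. How often each arm is asked, and when collection ends, are separate questions.

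**Working it through.** **1. Is the window really arm-specific?** Section 9.2.1 has one paragraph per arm. The CMT paragraph names a start (consent) and an end (six months). The usual-care paragraph names only the occasion of asking. So the protocol itself fixes a start for one arm and none for the other.

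**2. How could an earlier event reach the CMT record?** Section 9.2.2 has the physiotherapist ask about AEs at the start of each session, and section 8.7 aims for treatment to begin within 7 weeks of randomisation. No look-back period is given for that question. With a recording rule that starts at consent, an SAE from the consent-to-randomisation interval, if mentioned, has to be recorded. Usual care has only the six-month question. Both arms are referred to the same adverse-event question, and its recall period is not in the protocol.

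**3. Window length.** The protocol states no figure to reproduce. Let L be the lag in months from consent to randomisation. The typical lag is not given, so L is an assumption; section 8.7 permits up to 2 months before baseline collection in some cases.

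- Window as written for CMT: 6 + L months.
- Window from randomisation: 6 months.
- Ratio: (6 + L)/6. Share before randomisation: L/(6 + L).

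**4. Expected extra SAEs.** Section 10.1 gives 126 participants per group. The protocol gives no SAE rate, so r is assumed at 2%, 5% and 10% per person-year. Extra SAEs = 126 × r × L/12. This takes every participant to have lag L and every earlier event to be captured.

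| L (months) | Window | Ratio | Share before randomisation | Extra, r = 2% | Extra, r = 5% | Extra, r = 10% |
|---|---|---|---|---|---|---|
| 0.5 | 6.5 | 1.08 | 7.7% | 0.11 | 0.26 | 0.53 |
| 1 | 7 | 1.17 | 14.3% | 0.21 | 0.53 | 1.05 |
| 2 | 8 | 1.33 | 25.0% | 0.42 | 1.05 | 2.10 |

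Expected SAEs in the six months after randomisation are 126 × r × 0.5 = 1.26, 3.15 and 6.30 at the three rates. The excess is therefore about 0.1 to 2.1 events on a base of about 1.3 to 6.3.

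If the full 2-month delay were followed by the whole two-week reminder period, L would be about 2.5. The ratio would be 8.5/6 = 1.42, and the extra at r = 10% would be 126 × 0.10 × 2.5/12 = 2.6. That is an extreme case.

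**5. With a common start at randomisation** both windows are 6 months and the ratio is 1.00.

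**The case against.** **Recording is not analysis.** Section 9.2.1 governs what is recorded and reported, and section 10.5 does not list AEs or SAEs among the outcomes to be analysed. Which recorded events are tabulated by arm could be settled in a statistical analysis plan. This stands in part: nothing says outright that earlier events enter a between-arm count. But section 3.1 does promise treatment-effect estimates for adverse events, and the protocol has itself fixed a different window by arm, so the matter is not simply left open.

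**A reader might infer that earlier events are counted against CMT only.** The protocol does not show that for SAEs. Both arms answer the same six-month question. Depending on its recall period, usual-care participants might report earlier SAEs too, or the question might already be tied to randomisation.

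**A reader might extend the point to non-serious AEs.** Those have no usual-care counterpart at all, as section 9.2.1 openly says, and they count as an outcome only if attributed to the trial. An event before any CMT session is unlikely to be so attributed. Moving the start date would not make these counts comparable.

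**A reader might take Table 2 as a flat contradiction of section 9.2.1.** Table 2 shows when information is collected, which need not be the earliest permitted onset date. Both can hold, so the two are in tension and no more.

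**A reader might take 1.33 or 1.42 as the expected inflation.** Those ratios need the longest lag for every participant and fully one-sided capture. Section 8.7 allows the delay only in some cases, at sites with limited capacity.

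**The larger imbalance lies elsewhere.** CMT participants are asked at every session; usual care gets one questionnaire item. That is correct, and the protocol acknowledges it. The acknowledgement concerns contact during the intervention period, however, and gives no reason for a start before randomisation.

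**Conclusion.** The point holds in a limited form. The protocol sets a pre-randomisation start for the CMT arm's AE/SAE window and no start for usual care. Because SAEs of any cause are a secondary outcome, SAEs from before randomisation can enter the CMT count under a rule that usual care lacks. Whether usual care has an offsetting contribution cannot be determined without the recall period of the six-month question.

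The size is modest: for lags of 0.5 to 2 months, a window ratio of 1.08 to 1.33 and about 0.1 to 2.1 extra SAEs. This rests on an assumed common lag, assumed rates of 2% to 10% per person-year, 126 per arm, and full capture of earlier events in CMT with none in usual care. The true excess is likely to be towards the lower end, but with so few SAEs expected even one or two misplaced events would be visible. The defect is worth correcting because doing so is nearly free. It does not invalidate the safety data.

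**What to change.** - In section 9.2.1, state that the between-arm SAE summary counts events with onset from the date of randomisation to the six-month time-point, in both arms.
- Anchor the six-month adverse-event question to the participant's randomisation date, with the same wording in both arms.
- Keep recording consent-to-randomisation events for oversight if wanted, but list them separately and pooled, not by arm.
- Add a note to Table 2 so that its adverse-event row and section 9.2.1 give the same start.
- Keep non-serious AEs as a descriptive summary of the CMT arm.

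The cost is a sentence in section 9.2.1, a table note, a date in one question, and a comparison of onset date with randomisation date. No extra participant contact or visits are needed, so the protocol's concern about contaminating usual care does not arise. The revised wording would go through the amendment route in section 13.5. The change does not remove the difference in how often each arm is asked, which should be stated as a limitation wherever SAEs are compared.
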